Table 2: Reasons for using the CLAM-methode for measuring hip abductor/external rotator strength	

Different from the previously mentioned studies measuring with the CLAM-method, this study will use a “break test” instead of a “make test” and therefore measure eccentric rather than concentric muscle strength. Both methods in general show similar reliability (Conable & Rosner, 2011), but eccentric hip torque especially has been associated with functional capacity and pain levels in patients with AKP (de Marche Baldon et al., 2012; Nakagawa, de Marche Baldon, Muniz, & Serrão, 2011), and as the break test measures a complex proprioceptive response to changing pressure (rather than solely an isometric peak force), it seems to be a more valid method to measure functional impairments. Of course, even more meaningful would be strategies, that measure timing, activity level and capability to control movements of agonists and antagonists during different functional tasks, however, such methods would go beyond the scope of this dissertation.

[figure not shown]
Procedure:

Figure 2 illustrates the procedure of the proposed study. Researcher 1 (a physiotherapist trained in manual therapy, with seven years of clinical experience) will perform examination procedures and data collection (*Appendix 5*). If subjects agree to participate and meet inclusion criteria, they will be randomly assigned to either Group 1 or Group 2. Group 1 will receive the real intervention during the first period of measurement and a control/sham intervention one week later. Group 2 vice versa. Hence, each participant will serve as his/her own control group. As a simple randomization method is not recommended for a sample size of less than 100 (J. Kim & Shin, 2014), randomization sequence will be created using an online application called “Sealed Envelope” (Sealed Envelope Ltd, 2017) with random block

sizes of 4 and 6. This study will be double-blinded in the sense that both, subjects and the assessor of hip strength will be blinded to group assignment, whereas the therapist (Researcher 2), who carries out the interventions, will be the group allocator and not be blinded to group assignment.

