Torque measurement (Pre-Test) will be obtained by Researcher 1 (a physiotherapist trained in the use of a HHD; seven years of clinical experience) using the Clam-method (*Figure 1*). See *Appendix 5* for a detailed protocol. To maintain blinding, the subsequent interventions will be performed by Researcher 2, who will make sure that Researcher 1 has left the room. According to the respective group assignment, participants will either receive a hip joint mobilization or a sham intervention (see *Table 3* for a detailed description). All subjects will be re-tested (Post-Test) from Researcher 1 by using the same method as pre-intervention to establish post-intervention muscle strength immediately afterwards. In addition, Researcher 1 will use a scale to determine the subjective felt change in strength of participants and will assess the passive range of movement of the respective motions, which were restricted before the intervention, by using a digital goniometer.

One week later, the participants will be put through the same procedure again. Only this time, Group 2 will receive the real intervention, whereas Group 1 will get the placebo intervention.

INTERVENTION	JUSTIFICATION

Intervention
 
Passive hip joint mobilization: passive accessory movement on femur in anterior/posterior direction, grade III for four minutes and passive physiological movement of the most restricted hip joint movement, grade III for one minute (without pain).
	
The selection of this method of mobilization is not based on a theory of peripherally acting and specific biomechanical mechanisms. As Bialosky, Beneciuk et al. (2018) argue in their proposed model on mechanisms of manual therapy (MT), the literature does not support such a traditional mechanical theory. Their recent model rather suggests that a mechanical stimulus initiates a number of potential neurophysiological effects which produce the clinical outcomes associated with MT; the choice of technique does not seem to matter as much as identifying an individual likely to respond. That is why the inclusion criteria of this study are signs of hip impairment as well as no signs of other possible causes for gluteal inhibition/deconditioning

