Known intra-articular pathology: ligament and osteoarthritis ^{1,2,3,4,5}		
Patellar instability ^{1,4}		
Knee effusion ^{1,2}		
Patella subluxation/dislocation ^{1,3}		
Fat pad impingement/bursitis ^{1,5}		
Osgood–Scatter ^{1,2}		
OBJECTIVE TESTS:		
Symptom reproduction with (must be positive for at least one of the following activities)		
Squatting ^{1,2,3,4,5}		
Kneeling ^{1,2,3,4,5}		
Ascending or descending stairs ^{1,2,3,4,5}		
Positive for at least one of the following		
Patella compression test ^{1,4}		
Patella tilt test ^{1,4}		
OR		
(Minimum two out of three) positive for combination of		
Squatting ³		
Isometric quads ³		
Palpation of patella borders ³		
Excluded if positive for		
Lachmen's test ^{6,7,8}	ACL	
Posterior drawer test ^{6,8}	PCL	
Valgus stress test ^{6,8}	MCL	
Varus stress test ^{6,8}	LCL	
McMurray's test ^{6,8}	MENISCUS	
Patellar ballottement test ⁴	Effusion	

Figure 1: Checklist for diagnosis of anterior knee pain (Leibbrandt, Louw 2017)

Post-Test Data sheet:

Variable	Data
pretest_1_i	
pretest_1_ii	
pretest_1_iii	
pretest_1_pain	
posttest_1_i	
posttest_1_ii	
posttest_1_iii	
posttest_1_pain	
subj_change_1	
p_rom_change_1_*	
p_rom_change_1_*	
p_rom_change_1_*	
pretest_2_i	
pretest_2_ii	
pretest_2_iii	
pretest_2_pain	
posttest_2_i	
posttest_2_ii	
posttest_2_iii	
posttest_2_pain	
subj_change_2	
p_rom_change_2_*	
p_rom_change_2_*	
p_rom_change_2_*

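### The blinded strength assessor also collects felt change and hip motion at session 1, a possible cue to the session 2 treatment, and Appendix 6 gives the session 2 tests to the unblinded therapist

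*Combined protocol and SAP*

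**What the plan says.** The Procedure section describes the trial as double-blind in the sense that "both, subjects and the assessor of hip strength will be blinded to group assignment". The therapist, Researcher 2, allocates and treats and is not blinded. The safeguard it states for the assessor is: "To maintain blinding, the subsequent interventions will be performed by Researcher 2, who will make sure that Researcher 1 has left the room". The strength post-test then returns to the same person: "All subjects will be re-tested (Post-Test) from Researcher 1 by using the same method as pre-intervention".

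That person has two further tasks at the same visit: "In addition, Researcher 1 will use a scale to determine the subjective felt change in strength of participants and will assess the passive range". The second task covers only the hip motions found to be limited beforehand, and it is done with the goniometer. Table 3 says that the real arm includes "passive physiological movement of the most restricted hip joint movement, grade III for one minute". The sham is a grade I contact that meets no tissue resistance. One week later the procedure is repeated with the treatments exchanged.

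Appendix 9 provides one form, the "Post-Test Data sheet", for both sessions. The entries subj_change_1 and p_rom_change_1_* stand directly above pretest_2 and posttest_2. The Data Collection section makes Researcher 1 the recorder and says that only Researcher 2 knows the allocation. The variable list in Appendix 6, however, gives Researcher 2 as the collector for Pretest 2 and Posttest 2.

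**The concern.** Leaving the room stops the assessor from seeing the treatment, but not from learning about its apparent result. Felt change in strength, and motion in the very movements that only the real arm mobilises, could both differ between real and sham. With two sequences, a belief about session 1 carries over to session 2 with the treatment reversed.

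The strength test leaves room for such a belief to act. By the measurement protocol in the appendices, the examiner raises the force by hand, gives encouragement, and discards and repeats trials judged to show compensation. The session 2 post-test is half of each within-subject difference in the primary analysis. A shift that enters there cannot be separated from a treatment effect afterwards.

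The Appendix 6 entries raise a second, more direct problem: if they are followed, the person testing strength at session 2 knows the allocation.

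**Working it through.** The plan states no figure on this point. The check is therefore a trace of who learns what and when, followed by an illustration of size.

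**Trace**
- As described, the session 1 strength post-test comes before the felt-change and motion items. These items cannot affect the session 1 readings. The exposed readings are the pre-test and post-test of session 2.
- The Procedure and Data Collection sections point to Researcher 1 for all strength tests. Appendix 6 agrees for session 1 and names Researcher 2 for session 2. Both cannot be right.

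**Effect of a shift.** Let τ be the true difference, real minus sham, on the post-test. Suppose every guess is correct and session 2 readings move by b towards the guess (up for real, down for sham).
- Group 1 (real, then sham): period 1 minus period 2 = τ + b.
- Group 2 (sham, then real): period 1 minus period 2 = −(τ + b).
- Treatment estimate, half the difference between groups: τ + b.
- Sums of the two post-tests: −b in group 1 and +b in group 2, a difference of 2b.

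If a fraction p of guesses is correct, the bias is (2p − 1)b, which is zero at p = 0.5.

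**Inputs.** The within-patient variance of 2.1 comes from the Sample size Calculation section and is read here as kgf². The planned total is 20, taken as 10 per group. The test is the planned unpaired t-test, taken as two-sided at 0.05 with 18 degrees of freedom. The values of b and p are assumptions, because the documents give neither.

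Variance of a within-subject difference = 2 × 2.1 = 4.2. SE of the treatment estimate = √[(4.2/10 + 4.2/10)/4] = √0.21 = 0.458 kgf.

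**False-positive rate when τ = 0** (noncentral t with noncentrality (2p − 1)b/0.458):

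| Correct guesses | b = 0.25 kgf | b = 0.5 kgf | b = 0.75 kgf |
|---|---|---|---|
| 60% | 5.1% | 5.5% | 6.1% |
| 70% | 5.5% | 7.0% | 9.5% |
| 80% | 6.1% | 9.5% | 15.4% |
| 100% | 8.1% | 17.9% | 34.1% |

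A simulation of the planned test that draws the guesses at random gives closely similar values, for example 5.6% at p = 0.6 and 6.8% at p = 0.7 with b = 0.5.

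**How good a guess might be.** If one cue separates real from sham by s standard deviations, the chance of a correct guess is Φ(s/2): 56% at s = 0.3, 60% at 0.5, 66% at 0.8 and 69% at 1.0. The documents give no value of s.

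**Would the carryover test show it?** The variance of a patient's sum is 4 × (between-patient variance) + 4.2, so the SE of the difference in mean sums is √[2 × (that variance)/10]. Take b = 0.5 and all guesses correct, so that 2b = 1.0 kgf:
- between-patient variance 0: SE 0.917, rejection 18%;
- 2.1 (assumed): SE 1.587, rejection about 9%;
- 9 (assumed): SE 2.835, rejection about 6%.

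**The case against.** A reader might infer that the assessor is in effect unblinded, and that the false-positive rate is therefore 8% to 34%. The documents do not support this.
- They give no expected felt change or motion change by arm.
- Felt change is reported by participants who are themselves meant to be blinded, and the sham matches duration, setting, therapist and explanation.
- Table 1 puts the minimal detectable change for hip goniometry at 4 to 11 degrees, though it says that the digital device did better. The restricted movement receives one minute of mobilisation, so a motion reading may be a weak cue.
- The 8% to 34% range needs every guess to be correct and acted on. At 60% to 70% correct, most of the inflation disappears.

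Two further inferences also go too far. One is that the completed session 1 entries lie before the assessor at session 2: the form layout allows this, but no section says so, and records are to be locked away following the measurements. The other is that the plan would read the shift as carryover: the sums test would usually miss it.

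The measurement protocol also limits examiner influence through a marked landmark, a fixed instruction, consistent encouragement and the mean of three trials. The procedure figure and part of the appendices were not available here, so a safeguard stated only there cannot be ruled out.

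These objections limit the size, and they stand. They do not remove the pathway, because the same person holds both roles and the form spans both sessions. Nor does Appendix 6 rescue the plan by naming another tester, since that tester knows the allocation.

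**Conclusion.** The point holds in a limited form. The plan gives its blinded strength assessor a possible better-than-chance cue to the session 2 treatment, before the last examiner-dependent tests. It does not show that the assessor will be unblinded, and the bias cannot be sized from the documents.

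Under the stated assumptions the inflation is slight at 60% correct guesses and reaches 9.5% at 70% with the largest shift considered. The illustration is on the raw kgf scale. It rests on a variance from four healthy volunteers with an ambiguous unit, whereas the analysed outcome is normalised for body size. If 2.1 were a standard deviation, the SE would be √[(8.82/10 + 8.82/10)/4] = 0.66 kgf and the inflation for the same b would be smaller. The rates also ignore the plan's rule that a significant sums test stops the treatment comparison.

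The Appendix 6 conflict needs no assumption about guessing. As written, it contradicts the Procedure and Data Collection sections on who tests strength at session 2, and it should be resolved first.

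**What to change.** 1. Reconcile Appendix 6 with the Procedure and Data Collection sections so that the blinded Researcher 1 does all strength tests in both sessions.
2. Split the Appendix 9 form into one sheet per session. Seal the session 1 sheet and keep it unavailable at session 2. This also withholds the session 1 strength readings.
3. Have the participant complete subj_change on a slip that stays sealed until after session 2. Ask participants not to discuss the treatment with Researcher 1.
4. After the strength test, record post-intervention motion in absolute degrees, working from a list of the motions to re-measure without their baseline values. Calculate change after session 2.

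The cost is a redesigned form, a participant slip, corrected entries in Appendix 6 and a short addition to the Procedure section. No staff, visits or measurements are added, and every planned variable is kept. The downside is that Researcher 1 cannot check session 1 entries at session 2.

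The cue is reduced, not removed: Researcher 1 still takes the session 1 strength and motion readings, did the first examination, and may remember them.

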Prior to measurement, a mark will be placed five centimeters proximal to the middle of the knee joint line (along the body's longitudinal axis), to provide a consistent landmark for dynamometer placement. The CLAM-method will be performed with the participant in side-lying, with both legs positioned at 45° of hip flexion and 90° of knee flexion, with the limb to be tested superior (Figure 1). The participant will be instructed to lift the knee of the superior leg as far as possible while keeping the heels in contact, without allowing any compensatory movements. Following a warm-up consisting of one submaximal and one maximal practice trial, participants will perform three measurements with isometric contraction at their maximum exertion (with a 30 seconds rest between each trial). The instructions for the break test will be "Push as hard as you can; now don't let me move your leg." Consistent verbal encouragement will be provided during the slow increase of the applied force, until the resistance of the participant gets broken. Mean values will be calculated for each participant. If compensation movements are present, values will be discarded and a new measurement will be done after 30 seconds. No feedback (regarding their torque measure) will be provided to the subjects during the testing period.

Appendix 6

Variable list of the proposed study:

Nr	Abbreviation	Variable	Level of Measurement	Domain/Coding	Stage of measurement and Collector of data	Reason for measurement
1	id	Identification number of participant	nominal	0-20	Group Allocation stage. Researcher 2	Statistical analysis
2	group	Group affiliation of participant	nominal	1 = first session intervention, second session placebo 2 = vice versa		Methodology of study
3	female	Gender of participant	nominal	0 = male 1 = female	Examination stage. Researcher 1	Description of sample
4	age	Age of participant	metric	Integral Numbers		Description of sample
	right	affected side	nominal	0 = left 1 = right		
5	weight	Weight of participant	metric	Integral Numbers (in kg)		Normalization of Outcome measure
6	height	Height of participant	metric	Integral Numbers (in cm)		Normalization of Outcome measure
7	checklist	checklist for diagnosis of AKP	nominal	0 = fulfils checklist 1 = does not fulfil checklist		assessment of inclusion/exclusion criteria
8	slsq	Quality of single leg squat	nominal	0 = normal 1 = impaired		assessment of inclusion criteria
9	strength	Strength of hip abd/er	nominal	0 = normal 1 = weak		assessment of inclusion criteria
10	flex_l	ROM hip flexion, L	metric	Integral Numbers (in degree)		
11	flex_r	ROM hip flexion, R	metric	Integral Numbers (in degree)		
12	er90_l	ROM hip ER/90, L	metric	Integral Numbers (in degree)		
13	er90_r	ROM hip ER/90, R	metric	Integral Numbers (in degree)		
14	ir90_l	ROM hip IR/90, L	metric	Integral Numbers (in degree)		

15	ir90_r	ROM hip IR/90, R	metric	Integral Numbers (in degree)		assessment of inclusion criteria		
16	abd_l	ROM hip abd, L	metric	Integral Numbers (in degree)				
17	abd_r	ROM hip abd, R	metric	Integral Numbers (in degree)				
18	add_l	ROM hip add, L	metric	Integral Numbers (in degree)				
19	add_r	ROM hip add, R	metric	Integral Numbers (in degree)				
20	ext_l	ROM hip ext, L	metric	Integral Numbers (in degree)				
21	ext_r	ROM hip ext, R	metric	Integral Numbers (in degree)				
22	er0_l	ROM hip ER/0, L	metric	Integral Numbers (in degree)				
23	er0_r	ROM hip ER/0, R	metric	Integral Numbers (in degree)				
	ir0_l	ROM hip IR/0, L	metric	Integral Numbers (in degree)	Pretest 1. Researcher 1	determining torque values before intervention		
	ir0_r	ROM hip IR/0, R	metric	Integral Numbers (in degree)				
24	pretest_1_mean	mean of strength tests of hip abd/er of affected side (first period)	metric	0.4 to 135 (in kilograms force with 0.1 increments)				
	pret-test_1_i							
	pret-test_1_ii							
	pret-test_1_iii							
25	pretest_1_pain	reportment of pain during pretest (first period)	nominal	0 = no pain 1 = pain			for interpretation of results (later in the discussion section of this study)	
26	posttest_1_mean	strengthtest after intervention (first period)	metric	0.4 to 135 (in kilograms force with 0.1 increments)			Posttest 1. Researcher 1	determining torque values after intervention
	post-test_1_i							
	post-test_1_ii							
	post-test_1_iii							
27	posttest_1_pain	reportment of pain during posttest (first period)	nominal	0 = no pain 1 = pain	for interpretation of results			
	subj_change_1							
	p_rom_change_1_*							
	p_rom_change_1_*							
	p_rom_change_1_*							

28	pretest_2_mean	strength of hip abd/er with hhd of affected side (second period)	metric	0.4 to 135 (in kilograms force with 0.1 increments)	Pretest 2. Researcher 2	determining torque values before intervention
	pret-test_2_i					
	pret-test_2_ii					
	pret-test_2_iii					
29	pretest_2_pain	reportment of pain during pretest (second period)	nominal	0 = no pain 1 = pain		for interpretation of results
30	posttest_2_mean	strengthtest after intervention (second period)	metric	0.4 to 135 (in kilograms force with 0.1 increments)	Posttest 2. Researcher 2	determining torque values after intervention
	post-test_2_i					
	post-test_2_ii					
	post-test_2_iii					
31	posttest_2_pain	reportment of pain during posttest (second period)	nominal	0 = no pain 1 = pain		for interpretation of results
	subj_change_2					
	p_rom_change_2_*					
	p_rom_change_2_*					
	p_rom_change_2_*					

Appendix 7

Data Management Plan

1. What data will you collect or create?

see appendix 6

2. How will your data be documented and described?

see appendix 6

3. How will you deal with any ethical and copyright issues?

see "Ethical Considerations" (proposal)

4. How will your data be structured, stored, and backed up?

see "Data Collection" (proposal)

5. What are your plans for the long-term preservation of data supporting your research?

see "Data Collection" (proposal)

6. What are your plans for data sharing after submission of your thesis?

see "Reporting" (proposal)

Appendix 8

MA/MBA/MSc Dissertation Proposal

FACULTY OF HEALTH AND WELLBEING

PROJECT SAFETY PLAN: Risk Assessment Form

TITLE:	The immediate effects of passive hip joint mobilization on hip abductor/external rotator muscle strength in patients with anterior knee pain and impaired hip function	LOCATION:	[name]
PEOPLE AFFECTED:	Patients with anterior knee pain who meet inclusion criteria and agree to participate		
ASSESSMENT CARRIED OUT BY:	[name] (Physiotherapist) and [name] (Physiotherapist)		
PROJECT SAFETY OFFICER:			
SUPERVISOR:	[name]		
SIGNATURE OF SUPERVISOR		DATE:	

ACTIVITY	HAZARD ASSOCIATED WITH THE ACTIVITY	HAZARD RATING (High, Medium or Low)	CONTROL MEASURES TO BE TAKEN

Physical Examination procedure	Potential irritation/pain provocation/tissue damage of patient being examined	Low	The procedure will be conducted by an experienced physiotherapist in a clinical setting (physiotherapy practice) that conforms to the Austrian guidelines that are required for working with patients in a physiotherapeutic setting. If any signs of potential harm are present, the examiner will not perform any further tests and exclude the potential participant.
Manual muscle strength Test	Potential damage/physical overload due to maximal isometric contraction	Low	Patients with any relevant pathology (systemic diseases, severe osteoporosis, fractures..) or pregnancy will be excluded prior to the measurement. As the examiner is trained in the use of a HHD, there is no additional risk in using this apparatus within the strength test (other than it could be inconvenient for the patient on his/her skin, which will be checked with the patient). To ensure that the movement will be done correctly, two practice trials will be performed under the supervision of the researcher.
Passive hip joint mobilization	Potential irritation/pain provocation/tissue damage of patient being treated	Low	Again, performed by an experienced physiotherapist within a clinical setting. The intensity of the mobilisation will be moderate and without pain provocation. Patients will be encouraged beforehand to tell if anything is inconvenient for them. The screening/testing procedures and the interventions within this research project involve standard tests/techniques that any physiotherapist may conduct in the course of a clinical examination

Please keep this form in your Site File (Section 3 - Ethics) and update as appropriate.

Project Files and Site Files

All studies require a file with the administrative details such as letters and consent forms. If it is a non-NHS project then these are called 'project files', if an NHS project they are called 'site files'. They contain more or less the same things - for details see in the ethics folder on the BlackBoard site.

Appendix 9

First Contact/Examination Data sheet:

Variable	Data
id	
right	
female	
age	
weight	
height	
checklist_subj	
lumb_p	
ank_p	
pregn	
rel_dis	

Variable	Data	
checklist_obj		
slsq		
strength		
p_rom	left (_l)	right (_r)
flex		
er90		
ir90		
abd		
add		
ext		
er0		
ir0		

Checklist for diagnosis of anterior knee pain.		
SUBJECTIVE INFORMATION:		
Age (must be yes)		
14–50 ^{1,2,3,4,5}	YES	NO
Area (must be yes)		
Front of knee or retropatella ^{1,2,3,4,5}		
Chronicity		
Longer than three months ^{1,3,5}		
Aggravated by (must be yes for two or more of the following)		
Squatting ^{1,2,3,4,5}		
Prolonged sitting ^{1,2,3,4,5}		
Stairs (ascending or descending) ^{1,2,3,4,5}		
Kneeling ^{1,2,3,4,5}		
Excluded if any of the below is known		
Previous lower limb surgery ^{1,3,5}		
History of trauma ^{1,3,5}		
Rheumatological conditions ^{1,3,5}		
Known intra-articular pathology: ligament and osteoarthritis ^{1,2,3,4,5}		
Patellar instability ^{1,4}		
Knee effusion ^{1,2}		
Patella subluxation/dislocation ^{1,3}		
Fat pad impingement/bursitis ^{1,5}		
Osgood–Scatter ^{1,2}		
OBJECTIVE TESTS:		
Symptom reproduction with (must be positive for at least one of the following activities)		
Squatting ^{1,2,3,4,5}		
Kneeling ^{1,2,3,4,5}		
Ascending or descending stairs ^{1,2,3,4,5}		
Positive for at least one of the following		
Patella compression test ^{1,4}		
Patella tilt test ^{1,4}		
OR		
(Minimum two out of three) positive for combination of		
Squatting ³		
Isometric quads ³		
Palpation of patella borders ³		
Excluded if positive for		
Lachmen's test ^{6,7,8}	ACL	
Posterior drawer test ^{6,8}	PCL	
Valgus stress test ^{6,8}	MCL	
Varus stress test ^{6,8}	LCL	
McMurray's test ^{6,8}	MENISCUS	
Patellar ballottement test ⁴	Effusion	

Figure 1: Checklist for diagnosis of anterior knee pain (Leibbrandt, Louw 2017)

Post-Test Data sheet:

Variable	Data
pretest_1_i	
pretest_1_ii	
pretest_1_iii	
pretest_1_pain	
posttest_1_i	
posttest_1_ii	
posttest_1_iii	
posttest_1_pain	
subj_change_1	
p_rom_change_1_*	
p_rom_change_1_*	
p_rom_change_1_*	
pretest_2_i	
pretest_2_ii	
pretest_2_iii	
pretest_2_pain	
posttest_2_i	
posttest_2_ii	
posttest_2_iii	
posttest_2_pain	
subj_change_2	
p_rom_change_2_*	
p_rom_change_2_*	
p_rom_change_2_*
